9.2 ENTRY CRITERIA

9.2.1 Inclusion Criteria

1. The subject must provide written informed consent prior to any study related procedures.
2. The subject must be a female subject aged 18 years to 49 years inclusive.
3. The subject must have had her most recent surgical and – if available – histological diagnosis of pelvic endometriosis (laparoscopy, laparotomy, vaginal fornix or other biopsy) up to 10 years before screening.
4. The subject must agree to the washout intervals for prohibited therapies (if applicable).
5. The subject must agree to switch from her usual analgesic rescue medication to only those permitted by the protocol during the Screening, Treatment and Follow-up Period.
6. The subject has moderate to severe EAP during the screening period defined as:
 - a. At the screening visit, a score of at least 2 for DYS and at least 2 for NMPP for the previous month assessed with the modified Biberoglu & Behrman (mB&B) scale.

- b. Over two full menstrual cycles (i.e. from day 1 of the first menstruation going over two spontaneous menstrual cycles up to the day before the next menstruation i.e. the third menstruation) finishing just before the baseline visit:
 - i. Mean overall pelvic pain scores of at least 4 on the 0–10 NRS over the 5 days with the highest score for each cycle separately, i.e. required for both cycles;
 - ii. At least two days with “moderate” or “severe” pain on the 0–3 VRS for pelvic pain over the days with uterine bleeding for each cycle separately, i.e. required for both cycles;
 - iii. At least two days with “moderate” or “severe” pain on the 0–3 VRS for pelvic pain over the days without uterine bleeding for each cycle separately, i.e. required for both cycles.
7. The subject is compliant with eDiary completion i.e. has completed at least 75% of days during the screening period.
8. The subject has regular menstrual cycles and the total length of the two screening menstrual cycles should be between 42 and 76 days inclusive.
9. The subject has a Body Mass Index (BMI) $\geq 18 \text{ kg/m}^2$ at the screening visit.
10. If of childbearing potential, the subject agrees to use one of the following birth control methods during the Screening Period, the entire Treatment Period of the study and until 3 months after the end of treatment:
 - a. Sexual abstinence, if this is the subject's habitual practice and/or the subject is routinely abstinent from heterosexual intercourse,
 - b. Partner with a vasectomy with confirmed azoospermia,

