The analysis of the proportion of subjects reporting no analgesic use for EAP, and the proportion of subjects reporting no opiate use for EAP during the preceding 4-week period at Month 6 (last 28 days prior to and including last treatment administration date) will be conducted using a logistic regression model, with treatment group as the main effect (three values).

In addition to analgesic use for EAP as collected in the eDiary, concomitant medications in the study will be reviewed and medications to be considered as analgesic use for endometriosis associated pain will be confirmed by the Sponsor and be provided in an excel file prior to Database Lock. They may include any

Sponsor:	ObsEva		
Protocol:	18-OBE2109-003		
Document Version No.:	V5.0	Document Date:	13-JUN-2022

medication with the ATC codes from WHO drug dictionary version March 2016 as listed in Table 6 in Section 4.6.2.2.

In addition to analyzing the absence of analgesic use for EAP, the amount used for each 4-week period up to Month 6 will be summarized as a continuous variable, including the change from baseline. This analysis will be based on e-diary data only, as subjects did not record opioid intake in the concomitant medication page on a tablet-by-tablet basis.

As it is likely that more than one opioid will be used (opioid analgesic may be different depending on countries), the amount of opioid used will be converted to morphine milligram equivalents (MME) in order to better quantify the actual amount of opioids used by subjects.

For countries (Spain, Hungary, France, Czech Republic) where several opioids with different MME were allowed, the data collected in the e-diary is not sufficient to determine exactly which opioid was used and what the MME is. The MME will be derived as the average of possible MME of the allowed opioids in the country.

No opioids are allowed in Ukraine. Subjects from Ukraine will therefore be excluded from the summary in MME. If some opioids are nevertheless recorded for subjects from Ukraine, they will not be considered for the summary in MME, as the conversion in MME would be unknown. Those opioids records will however be considered for other analgesic use analyses not requiring conversion in MME.

The baseline amount of analgesic used will be computed by averaging the amount used during the two baseline menstrual cycles.

Conversion to MME by country is described in Table 7.

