Corresponding baseline values will be calculated based on the two baseline menstrual cycles, which may not be exactly 28 days each.

The values for other endpoints (monthly and 3-monthly questionnaires from Section 4.6.4.19 to Section 4.6.4.26) are defined as the value at the corresponding visit or value falling into the corresponding visit window as described in section 4.2.9. For these other endpoints, descriptive summaries by visit will be

Sponsor:	ObsEva		
Protocol:	18-OBE2109-00	3	
Document Version No.:	V5.0	Document Date:	13-JUN-2022

performed in two ways, once including values at the corresponding visit or value falling into the corresponding visit window as described in section 4.2.9, and once applying the while on treatment strategy, i.e., including values from the discontinued visits at each next scheduled visit.

For endpoints based on daily diary data, analyses will use observed data only in such cases, provided that a minimum number of 43% (at least 12 days of each 28-day period) completed daily eDiary entries are available.

4.6.4.1. Clinically meaningful reduction at scheduled visits other than Month 3 for DYS and NMPP

The proportion of responders for DYS and NMPP based on daily e-diary data will be reported at each visit (each 28 days period) along with odds-ratio and 97.5% confidence intervals from logistic regression as described in Section 4.6.2.1.2.

The same responder definition defined for primary endpoint in Section 4.6.2.1.1 will be used, but for other scheduled visits.

Due to the war situation in Ukraine, data from subjects in Ukraine sites may be incomplete, missing or uncleaned. The descriptive analysis of proportion of responders for DYS and NMPP at each visit will be repeated, excluding data collected after 24FEB2022 for subjects from Ukraine sites, for the Follow-up period only (Follow-up set), as the main treatment period was completed before the start of the war. Listings will contain country information to identify those subjects.

4.6.4.2. Change from baseline to each scheduled assessment in mean pelvic pain scores for DYS, NMPP and overall pelvic pain, during the previous 4-week period assessed on the NRS and VRS

The change from baseline to each scheduled assessment in mean pelvic pain scores for DYS, NMPP and overall pelvic pain will be analyzed as described for the ranked secondary endpoint in Section 4.6.3.1 (continuous summary and analysis of covariance at each visit).

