4.6.4.3. Change from baseline to each scheduled assessment in the number of days with moderate to severe pelvic pain during the previous 4-week period assessed on the VRS

The actual value and change from baseline of number of days with moderate or severe pelvic pain collected in the e-diary on the VRS will be summarized for each 28-day period. The baseline value will be computed by averaging the number of days with moderate or severe pelvic pain of the two baseline menstrual cycles. The number of days will be analyzed with a negative binomial model including baseline

Sponsor:	ObsEva		
Protocol:	18-OBE2109-003		
Document Version No.:	V5.0	Document Date:	13-JUN-2022

as a covariate. The estimated least square means treatment differences along with 97.5% CI will be provided.

SAS Code for negative binomial model with repeated measurements

```
proc genmod data=dataset order=internal ;
    class treatment;
    model nbdays = baseline treatment / dist=negbin type3 ;
    lsmeans treatment / diff = control('1') exp at means cl alpha=0.05
adjust=bon;
estimate 'TRT Placebo' intercept 1 base %sysevalf(&meanbase.) trt01pn 1 0 0 /
exp E;
estimate 'TRT LGX 75' intercept 1 base %sysevalf(&meanbase.) trt01pn 0 1 0 /
exp E;
estimate 'TRT LGX 200' intercept 1 base %sysevalf(&meanbase.) trt01pn 0 1 0 /
exp E;
estimate 'TRT LGX 200' intercept 1 base %sysevalf(&meanbase.) trt01pn 0 1 0 /
exp E;
estimate 'TRT LGX 200' intercept 1 base %sysevalf(&meanbase.) trt01pn 0 0 1
/ exp E;
    ods output lsmeans=lsm diffs=lsmd Estimates=estimate ;
```

run;

"meanbase" macro variable is the mean value of baseline over the same selection of subjects used in the model

4.6.4.4. Change from baseline to each scheduled assessment in the mean worst pelvic pain score defined as the mean of the 5 highest daily pain scores reported during the previous 4-week period assessed on the NRS

The actual value and change from baseline of the mean worst pelvic pain score, defined as the mean of the 5 highest daily pain scores reported during each 28-day period will be summarized for each 28-day period. The baseline mean worst pelvic pain score will be the average of the mean pelvic pain score of each of the two baseline menstrual cycles. An analysis of covariance will be performed for each period.

If less than 5 days of pain score data is available, the mean worst pelvic pain will be defined as the mean of the available daily pain scores.

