The actual value and change from baseline of number of days with answer to Sexual Intercourse in the last 24H questionnaire is "Intercourse was interrupted due to pain" or "No, I avoided sexual intercourse because of anticipation of pain" collected in the e-diary will be summarized for each 28-day period. The number of days will be analyzed with a negative binomial model, including baseline as a covariate. The

Sponsor:	ObsEva			
Protocol:	18-OBE2109-00	18-OBE2109-003		
Document Version No.:	V5.0	Document Date:	13-JUN-2022	

estimated least square means treatment differences along with 97.5% CI will be provided. The baseline value will be computed by averaging the number of days of the two baseline menstrual cycles.

4.6.4.15. Change from baseline to each scheduled assessment in the number of days when sexual intercourse was avoided because of anticipation of pain during the previous 4-week period as assessed on the dyspareunia VRS

The actual value and change from baseline in the number of days with answer to Sexual Intercourse in the last 24H questionnaire is "No, I avoided sexual intercourse because of anticipation of pain" collected in the e-diary will be summarized for each 28-day period. The number of days will be analyzed with a negative binomial model, including baseline as a covariate. The estimated least square means treatment differences along with 97.5% CI will be provided. The baseline value will be computed by averaging the number of days of the two baseline menstrual cycles.

In addition, the proportion of days when sexual intercourse was avoided because of anticipation of pain will be also summarized for actual values and changes from baseline.

The proportion is defined as:

Number of days when sexual intercourse was avoided because of anticipation of pain/ (Number of days in period – Number of days with missing data – Number of days with no sexual intercourse for other reasons)

The number of days in each period will be equal to 28, except at baseline, for which it will be the number of days in each baseline menstrual cycle.

4.6.4.16. Change from baseline to each scheduled assessment in the number of days with uterine bleeding (including spotting) during the previous 4-week period measured by eDiary

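### Day-count endpoints set a raw count per menstrual cycle (mean length 21 to 38 days) against a count per 28 days, which distorts the within-arm changes from baseline

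*SAP*

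**What the plan says.** Protocol 7.1.2.2 lists a series of endpoints that are changes from baseline in a number of days over the preceding 4 weeks. SAP 4.6.4 gives the derivations.

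- **Baseline.** For moderate or severe pain days (4.6.4.3): "The baseline value will be computed by averaging the number of days with moderate or severe pelvic pain of the two baseline menstrual cycles". The rule is repeated, with the event changed, for analgesic days (4.6.4.9), opioid days (4.6.4.10, listing only), pain-free days (4.6.4.11), days without difficulty in activities (4.6.4.13), the two dyspareunia counts (4.6.4.14, 4.6.4.15), bleeding days (4.6.4.16), missed school or work (4.6.4.17) and days lying down (4.6.4.18). That makes nine summarised and modelled endpoints and one listing.
- **On study.** The actual value and the change "will be summarized for each 28-day period".
- **Cycle length.** Inclusion criterion 8 (Protocol 9.2.1) requires that "the total length of the two screening menstrual cycles should be between 42 and 76 days inclusive". SAP 4.6.4 recognises the inequality: "Corresponding baseline values will be calculated based on the two baseline menstrual cycles, which may not be exactly 28 days each". No rescaling of the counts follows.
- **One exception.** SAP 4.6.4.15 adds a proportion of days, whose period length is "equal to 28, except at baseline, for which it will be the number of days in each baseline menstrual cycle".
- **Model.** The sample code in 4.6.4.3 reads "model nbdays = baseline treatment / dist=negbin type3".
- **Analgesic amounts.** In SAP 4.6.3.6, "the amount used for each 4-week period up to Month 6 will be summarized as a continuous variable, including the change from baseline", and the baseline amount is an average over the two cycles. SAP 4.6.4.7 and 4.6.4.8 use mean daily pill count and mean daily morphine equivalents instead.

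**The concern.** A mean daily score does not depend on how many days it covers; a count does. The baseline count accrues over one cycle and the on-study count over 28 days, so their difference mixes any treatment effect with cycle length. This happens even when every diary entry is complete, so it is separate from missing diary days.

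Two things are at stake. The within-arm changes from baseline are planned outputs for all nine summarised endpoints, and they would not measure the 4-week change that the protocol defines. For pain-free days the sign is awkward: a woman with long cycles appears to worsen when nothing has changed. The baseline covariate is also noisier than it need be, which costs precision in the comparison between arms.

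**Working it through.** The plan states no figure for this, so there is none to reproduce.

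**Inputs.** Two-cycle total of 42 to 76 days (Protocol 9.2.1, criterion 8), so mean cycle length L runs from 42/2 = 21 to 76/2 = 38 days. On-study period: 28 days (SAP 4.6.4). The daily event rate r is not given in the documents; I assume it is constant and show a range.

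**Formula.** Baseline = r x L and on-study value = r x 28. The spurious change is r x (28 - L). As a share of baseline it is (28 - L)/L, which does not depend on r.

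| L (days) | Change, % of baseline | r = 0.3 (days) | r = 0.5 (days) |
|---|---|---|---|
| 21 | +33.3 | +2.1 | +3.5 |
| 26 | +7.7 | +0.6 | +1.0 |
| 28 | 0 | 0 | 0 |
| 30 | -6.7 | -0.6 | -1.0 |
| 35 | -20.0 | -2.1 | -3.5 |
| 38 | -26.3 | -3.0 | -5.0 |

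**Effect on the comparison between arms.** This was checked by an illustrative simulation with no treatment effect: 150 per arm, L uniform from 21 to 38, daily rate Beta(4,6), a negative binomial model with fixed dispersion, 1,000 runs. All of these are assumptions except the arm size.

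- Mean change in the placebo arm: about -0.6 days. This agrees with the formula: mean rate 4/10 = 0.4, mean L = (21 + 38)/2 = 29.5, and 0.4 x (28 - 29.5) = -0.6.
- Log rate ratio between arms: -0.001 with the raw baseline and -0.001 with the baseline scaled to 28 days, so no bias with either.
- Empirical standard error of the log rate ratio: 0.038 raw, 0.033 scaled.

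**Check of possible remedies.** Take r = 0.5, a 28-day cycle, 75% diary completion in both periods and no true change. Each period then has 21 diary days and 10.5 events.

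- Current rule: 10.5 to 10.5, change 0.
- Baseline alone scaled by diary days: 28 x 10.5/21 = 14, against 10.5 on study, a spurious -25%. With only 12 of 28 on-study days completed (the SAP minimum) it is 14 to 6, or -57%.
- Both periods scaled by diary days: 14 to 14, change 0.
- Baseline x 28 / cycle length, on-study count raw: 10.5 to 10.5, change 0.

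**The case against.** The strongest reply is that little depends on this. The endpoints are additional secondary ones outside the fixed sequence. The tested outcome is the 28-day count, not the difference. Both documents disclose that cycles need not last 28 days, actual values are reported beside the changes, and 4.6.4.15 already has a length-adjusted proportion. The largest shifts need both cycles together to lie at an eligibility limit. Shifts of opposite sign partly cancel within an arm, and even a wide uniform spread of cycle lengths moved the arm mean by only about -0.6 days.

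Most of that stands, and it limits the point to descriptive changes and some precision. Disclosure does not correct the derivation, though, and the 4.6.4.15 proportion serves one endpoint of nine. The SAP has accepted the principle elsewhere: its V3.0 change log (SAP section 5) replaced total pill counts and morphine equivalents by daily means so as to adjust for missing days, and the day counts were left as they were.

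A reader might infer three stronger things that the documents do not support.

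- **That the treatment comparison is biased.** Cycle length is fixed before randomisation and baseline is a covariate, not subtracted, so it is not.
- **That losses, like gains, reach a third of baseline.** The largest loss is 26%. It is 36% (10/28) only when expressed against the 28-day value.
- **That analgesic amounts are affected generally.** The primary endpoint, 4.6.4.7 and 4.6.4.8 use daily means. Only the summary in 4.6.3.6 is in question, and its text does not say whether the averaged baseline amount is a total per cycle or a daily mean.

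**Conclusion.** The point holds for the day counts in SAP 4.6.4.3, 4.6.4.9, 4.6.4.11 and 4.6.4.13 to 4.6.4.18, and for the listing in 4.6.4.10. Followed as written, the plan reports a non-zero change for a woman whose daily rate is unchanged whenever her mean cycle length differs from 28 days. The limits are +33% and -26% of baseline at the eligibility bounds; near 28 days the shift is a few percent. The primary and ranked secondary tests are untouched.

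The percentages rest on a constant daily rate and nothing else. The shifts in days also depend on the assumed rate. The arm-level shift and the precision loss depend on an assumed cycle-length distribution that the documents do not give. For bleeding days the proportional argument holds only on average, because a 28-day window may contain no menses, one or two. The correction should be made, but it does not threaten the trial's main conclusions.

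**What to change.** Add one sentence to SAP 4.6.4 putting both periods of every day-count endpoint on the same 28-day basis, in one of two ways:

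1. 28 x events / completed diary days, for baseline and for each on-study period alike. This also deals with missed entries and with on-study windows cut short by early discontinuation.
2. At minimum, baseline count x 28 / cycle length, with the on-study count left as it is.

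Do not scale baseline alone by diary days. Use the scaled baseline both for the change and as the covariate. Under option 1 the scaled on-study value need not be a whole number, so in the negative binomial model keep the raw count and use the log of completed diary days as an offset. Note for 4.6.4.16 that scaling bleeding days is right only on average. In 4.6.3.6, state the analgesic amount as a mean daily amount in both periods, as in 4.6.4.7 and 4.6.4.8.

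The cost is a sentence or two and one derivation line per endpoint, with no new data: SAP 4.5.2 already derives the cycle durations. SAP 4.3 allowed unblinded results to reach the sponsor once the Month 6 thresholds were in the SAP, and V5.0 follows that update. If Month 6 results have been seen, label the change as a correction and show both versions. Because cycle length precedes randomisation, rescaling cannot systematically favour an arm.
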